2.3. Study Objectives

- Primary Objective:
 - To assess the impact of SU treatment on Progression Free Survival (PFS) and on Time to Treatment Failure (TTF) for patients with adv/ mRCC.
- Secondary Objectives:
 - To assess the Objective Response Rate (ORR) for adv/ mRCC patients receiving SU as 1st line treatment.
 - To describe the usage of different doses of SU in these patients in terms of: dosing change, dosing schedules and the average dose received during the SU period treatment
 - To assess the impact of the 2nd line sequence SU- different treatment on combined PFS and TTF for patients with adv/mRCC and according to the second line post SU treatment (TK1,mTOR)
 - To describe the safety of 2nd line SU-different sequence treatment and the tolerability of patients receiving it.
 - To measure Quality of Life (QoL) of the patients
 - The following treatment outcomes will also be assessed:
 - Treatment patterns (dose/ duration) for SU
 - Patterns of toxicity exhibited by patients

3. Interim and Final Analysis

- A final report will address the study objectives through detailed analysis of the efficacy and safety endpoints as advised by the protocol.
- There will be no interim analysis for this study.

4. Hypothesis and Decision Rules

- Descriptive and hypothesis testing will be applied for presenting and analysis data
- For all comparisons, the significance threshold will be set at the commonly used 5% level. The type I error will not be adjusted for multiplicity
- Summary tables will contain footnotes in the body of the title that reference any data listings or tables associated with the table or figure (e.g. Reference: Listing 16.X.XX).
- All means and medians will be formatted to one more decimal place than the measured value. Confidence intervals and standard deviation values will be formatted to two more decimal places than the measured value. Minimum and maximum values will be presented with the same number of decimal places as the measured value.
- The number and percentage of responses will be presented in the form XX (XX %) where the percentage as whole numbers will be in parentheses.
- All p-values will be presented with at least 3 decimal places ensuring meaningful representation.

- All summary tables will include the total number of subjects in the population that is being analysed
- Analysis population and subgroups

4.1. Analysis sets

- **Setting population or full analysis set**

The setting population or full analysis set refers to all eligible patients enrolled in the study, whatever the therapeutic strategy used during the observation period

- **Target population :**

The target population are patients above 18 suffering from advanced mRCC and residing in AFME to whom the results of the study will be extrapolated

- **Efficacy population:**

Include full analysis set who received a dose of SU and continued at least 6 month follow up period

- **Safety population:**

Include full analysis set who exhibited any adverse event after the first dose of SU.

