3.3.3. End-points

Primary End-point:

1. Progression Free Survival (PFS) for patients with ad/mRCC receiving SU.

PFS is defined as: the time from when the patient receives the first dose of SU to the time of progression or death due to any cause, which occurs first.

2. Time to Treatment Failure (TTF) for SU 1st line.

TTF is defined as: from when the patient receives the first dose of SU to the time of SU discontinuation (date completed by the physician).

Secondary End-point:

1. Objective Response Rate (OOR) for adv/mRCC patients receiving SU as 1st line treatment.

ORR is defined as the percentage of patients with confirmed CR or confirmed PR according to RECIST criteria v1.1.

2. Description of SU real life usage of doses across all centers, including description of treatment schedules (dose change, dose schedule, average dose received during the period treatment).

3. Combined PFS for patients with ad/mRCC receiving the 2nd line sequence SU- different treatment.

Combined PFS is defined as: the time from when the patients receives the first dose of SU as first line, until progression or death due to any cause while on the 2nd line treatment, whichever occurs first during the 2nd line sequence treatment.

4. Combined TTF for the SU-2nd line sequence.

Combined TTF is defined: as the time from when the patient receives the first dose with SU as first line, to the time of 2nd line sequence discontinuation (date completed by the physician).

5. OS for adv/mRCC patients receiving SU as first line followed by 2nd line as measured from date of first SU dose to the date of death of any cause. The OS median and the overall survival at month 24 (24 months OS) will be measured.
6. If possible, efficacy parameters (PFS, OS) for the combined 1st line SU- 2nd line sequences according to the second line post SU (other than SU-AXI):
 - SU in 1st line-Axitinib TKI in 2nd line.
 - SU in 1st line- other TKI in 2nd line (sorafenib, pazopanib).
 - SU in 1st line/mTOR in 2nd line (temsirolimus, everolimus).
7. Safety description with AE listing in patients receiving SU: frequencies of patients experiencing at least one AE will be displayed by body system.
8. QoL using the questionnaire Functional Assessment of Cancer Therapy-Kidney Symptom Index 19 (FKSI-19).

CCI

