8.2. Setting

The study will enroll patients according to the eligibility criteria in participating countries across Africa Middle East. The recruiting centers will be representative of each country involved in terms of care management systems, of size and of practices (at least when performing feasibility).

Any patient who meets the eligibility criteria will be invited to participate in the study with no biased selection by the investigators. The enrollment visit will be performed at the time of the patients' inclusion, after the patients' acceptance of enrollment in the study.

Data will come from medical records and will be collected in routine clinical practice. The enrollment visit will comprise a first section on patients' eligibility for every patient whatever pool they belong to and a second section on SU treatment started at the inclusion.

Follow-up will be ensured during visits in the context of usual patients' care management (non-interventional study). No extra visits will be required by the protocol of the study.

As long as the patients are treated with SU as first line, every visit to the center will be recorded. In accordance with ESMO guidelines and physicians clinical practice is real life, follow-up visits are approximately expected:

- During SU treatment: every 6 weeks (every cycle) with tumor assessment approximately every 3 months with respect to the clinical practice.
- When patients come off SU treatment (and after receiving the SU-2nd line sequence) they will be followed-up every 6 months (separate form) for survival until the end of the study.
- A deviation of +/- 6 weeks (1.5 months) is acceptable window for the follow-up visits.

As the inclusion criteria (patients being treated with SU in 1st line according to the approved therapeutic indication), the medication prescribed within the regular practice of the physician. In addition, as of the non-interventional nature of the study, there will be no specific requirements with regards to the treatment process. The physician will determine dosage and duration of the treatment, guided by the local country approved Prescribing Information and according to his assessment of the individual therapeutic needs of the patient.

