2.2. Study Design

▪ Global design

- OPTIMISE is an international prospective, non-interventional, non-controlled, observational multicenter study.
- Patients would be enrolled from several AfME countries including Algeria, Morocco, Tunisia, Egypt, UAE, Qatar and South Africa.
- Investigators will be specialists in charge of adv/mRCC where sites involved will be representative of their respective countries in terms of practice
- Participating physicians will not be influenced in their decision making and routine practice in any way.

▪ Populations

- Patients will be enrolled when newly diagnosed and when the treatment with SU is chosen as 1st line
- Patients enrolled at SU initiation, will be followed-up whatever the post 2nd line SU- different sequence treatment is (AXI, other drugs, no further active treatment OR supportive care).
- The possible 1st and 2nd line sequences of treatment under investigation (i.e. patient pools) will be as follows:
 - SU-AXI
 - SU- other second line treatment (sorafenib, pazopanib, everolimus, temsirolimus, other)
 - SU- not further active treatment (supportive care)
- The population of interest has the below inclusion and exclusion criteria ;
Inclusion criteria:
 - Adult patients (males and females) 18 years of age and over.
 - Patients being treated with SU as 1st line treatment according to the approved therapeutic indication.
 - Histologically confirmed diagnosis of adv/mRCC (clear cell RCC as well as non-clear cell RCC) with measurable disease according to RECIST 1.1
 - Evidence of a personally signed and dated informed consent document
Exclusion criteria:
 - Patients being treated with cytokines or any other treatment other than SU
 - Patients presenting with a known hypersensitivity to SU or its metabolites will not be included in the study per the label.

▪ Data sources

- Data will be collected in routine clinical practice and from medical records
- A case report form (eCRF) will be used for data collection which should be signed by the investigator.
- An investigator performs an assessment of new or ongoing adverse events, relative to a patient's baseline history, at each study visit.
- Generally, the identification of new or ongoing adverse events is determined till the last scheduled visit. CTCAE version 4.0 will be used for the grading of AEs in the eCRF.

Observation period

- The inclusion period of eligible patients is planned for 12 months, with minimum of 1 year follow-up period.

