5.5. Covariates

- In case of multivariate analyses, baseline characteristics will possibly be used as covariates.
- The final covariates will be selected according to the selection strategy of variables defined in the part 7.6.
- Possible, but not exclusive, baseline covariates related to SU initiation will be limited because of a retrospective part of the data collection, with:
 - Age and sex;
 - ECOG (0, 1, 2, 3, 4), Karnofsky performance status
 - MSKCC risk factors (Favorable, Intermediate, Poor)

- Medical history of hypertension (Yes, No)
- Delay from diagnosis (< 1 year from diagnosis to first metastasis detection/ \geq 1 year)
- Nephrectomy (Yes, No)
- Number of metastatic sites
- The covariates identified previously will be also explored and act as baseline for second line treatment initiation. In this case, other covariates will be:
 - The response to SU treatment in 1st line;
 - Duration of SU treatment, PFS;
 - Previous treatments for primary tumor (surgery, radiotherapy, other);
 - Additional anti-tumor treatments;

6. Handling missing values

- The majority of data will be collected with a website (except for FKSI-19 questionnaires).
- In this website, the input of certain data will be obligatory, limiting the number of missing values, particularly for endpoints.
- Regarding the descriptive analyses of each variable, it will be based on the available data (“observed-case analysis”), considering missing data as non-informative.
- The number of missing data will be documented for each analysis.
- The analysis of the primary endpoint is a survival analysis which is known to efficiently handle missing data: All patients are included in the analysis and missing data are called right-censored data.
- In case of absence of 20% data and over, for a main parameter such as ORR rate, the Hot-deck imputation method could be used. With this method, the missing value is replaced by the observed value of a patient with similar characteristics $X_1, X_2 \dots X_k$. If it does not exist such similar patient, the missing value will be amputated
- A sensitivity analysis will be conducted by the imputation of extreme values. In the one hand, analysis in the most unfavorable situation (i.e. missing data considered as failure) and in the other hand, analysis in the most favorable situation, i.e. missing data considered as success (e.g. for ORR, success is to be responder).

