8.1. Efficacy analyses

8.1.1. Survival analyses

▪ Role:

- To meet primary and secondary objectives
- To assess the impact of SU as a first line therapy on progression free survival (PFS) and on time to treatment failure (TTF) for patients with adv/mRCC in real life setting;
- To assess the impact of the SU–other sequence on combined PFS and TTF for patients with adv/mRCC.
- To assess the Overall Survival (OS) (OS median and 24-month OS) for adv/mRCC patients receiving SU in first line followed by other sequence in 2nd line;
- To assess the time to strategy failure (TSF) for adv/mRCC patients receiving the SU–other sequence;
- To assess PFS and OS for the combined 1st line SU – 2nd line sequences according to the second line post SU (TKI, mTOR) treatment; (specific objective – “SU – TKI/mTOR” patients)

▪ Population:

- “SU – other sequence” patients
- “SU – TKI / mTOR” patients

▪ Endpoints:

- Progression Free Survival (PFS)
- Combined PFS
- Time to Treatment Failure (TTF)
- Combined TTF
- Time to Strategy Failure (TSF)

- Overall Survival (median OS and 24-month OS rate)
- **Subgroups:**
- Type of 2nd line treatment post SU: “SU – TKI / mTOR” patients (**SUT-TKI and SUT-mTOR**)
(only combined PFS and OS endpoints)
- **Statistical methods:** Survival analysis methods.
- **Method for handling missing values:** see guideline in chapter 7.

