8.1.2. Objective response rate

- **Role:**
- To assess the Objective Response Rate (ORR) for adv/mRCC patients receiving 2nd line post SU”
- **Population:**
Study population “SU – other sequence” patients
- **Endpoints:**
- Clinical Benefit Rate (CBR)
- Objective Response Rate (ORR)
- **Statistical methods:**
Descriptive analyses
- **Method for handling missing values:**
Hot-deck imputation method and imputation by extreme values

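### The SAP's only visible efficacy set requires 6 months of follow-up, which removes early deaths and conflicts with the populations named elsewhere in the SAP

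*SAP*

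**What the plan says.** SAP 4.1 first describes its broadest group of patients: "The setting population or full analysis set refers to all eligible patients enrolled in the study, whatever the therapeutic strategy used during the observation period". It then defines the one set labelled for efficacy: "Include full analysis set who received a dose of SU and continued at least 6 month follow up period".

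Other parts of the plan bear on the same analyses:

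- SAP section 6 (Handling missing values), on the primary endpoint: "All patients are included in the analysis and missing data are called right-censored data".
- SAP 8.1.1 lists first-line PFS and TTF among its aims, but gives the population as "SU – other sequence” patients" together with a TKI/mTOR group.
- SAP 8.1.2 gives, for ORR, "Study population “SU – other sequence” patients". Its stated role is ORR in patients on second-line treatment, whereas the objective in SAP 2.3 is ORR on first-line SU.
- Protocol 3.3.3 defines PFS as "the time from when the patient receives the first dose of SU to the time of progression or death due to any cause". OS also runs from the first SU dose. Neither definition has a 6-month condition.
- SAP 2.2 plans recruitment over 12 months "with minimum of 1 year follow-up period". Protocol 8.2 says of patients who have come off SU that "they will be followed-up every 6 months (separate form) for survival until the end of the study".

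Protocol 8.9 contains no 6-month restriction. It says that major changes to the primary endpoint analyses would be reflected in a protocol amendment.

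**The concern.** The clock for PFS, TTF and OS starts at the first dose, but membership of the efficacy set depends on what happens in the next 6 months. A death at month 3 is an event under the endpoint definitions, yet the patient is not in the set. Every patient in the set is alive at month 6 by construction. This is selection on survival (immortal time), and it pushes PFS and OS upward. TTF moves the same way when early deaths go with short treatment, and ORR does so when early deaths respond less often than others.

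In a single-arm study the absolute median or rate is the result, so the shift goes straight into the report. The SAP also gives three different descriptions of who is analysed. On the visible text, the choice between them could be made after the data are seen.

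**Working it through.** **1. Who fails the 6-month rule.** Planned follow-up is at least 1 year, so late enrolment cannot leave a patient short of 6 months. Progression or stopping SU does not by itself end follow-up (Protocol 3.5 and 8.2). That leaves deaths and study leavers before month 6. Simulating 10% non-informative dropout by month 6 and excluding only those patients left median PFS essentially unchanged (5.90 to 5.85 and 10.48 to 10.42 months). The bias therefore comes from deaths and from dropout related to outcome.

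**2. The plan's own figure.** Protocol 8.7: n = 1.96² × 0.37 × 0.63 / 0.08² = 139.9, so 140. This reproduces.

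**3. Model for the size of the effect.** The documents contain no PFS or OS assumptions, so the inputs are:

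- m, median time to first event: 5.9 and 10.5 months. These are the SU treatment durations quoted in Protocol 6.1.1, used as stand-ins.
- OS median: 18 and 24 months (assumed).
- d, share of first events that are deaths: 10% (assumed; 5% and 20% as sensitivity).

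With h = ln 2 / m and post-progression death hazard λ, survival is S(t) = e^(−ht) + (1−d)·h·[e^(−λt) − e^(−ht)]/(h−λ). λ is solved so that S equals 0.5 at the OS median.

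The share excluded is x = 1 − S(6). Among patients alive at month 6:

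- median PFS = m × [1 + log₂(1/(1−x))], valid when the result is at least 6 months
- 24-month OS = S(24)/(1−x)
- ORR = (0.37 − x·r)/(1−x), where r is the response rate among those excluded

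| | m = 5.9, OS median 18 | m = 10.5, OS median 24 |
|---|---|---|
| Excluded, x | 13.8% (about 19 of 140) | 8.7% (about 12 of 140) |
| Median PFS | 5.9 × [1 + log₂(1/0.862)] = 7.2 | 10.5 × [1 + log₂(1/0.913)] = 11.9 |
| 24-month OS, all treated | 0.360/0.862: 36% to 42% | 0.500/0.913: 50% to 55% |
| 24-month OS, patients who progressed | 39% to 44% | 53% to 57% |
| ORR 37%, r = 20% | 39.7% | 38.6% |
| ORR 37%, r = 0 | 42.9% | 40.5% |
| Patients left; ORR margin | 121; ±8.6 points | 128; ±8.4 points |

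Patients who progressed are a proxy for the protocol's OS group, which goes on to second-line treatment. The margin is 1.96 × √(0.37 × 0.63/n), against ±8.0 points at n = 140. In both columns about 73% of patients with a PFS event before month 6 stay in the set, so the rule removes early deaths rather than early progressors.

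**4. Sensitivity.** Over both values of m, both OS medians and d of 5%, 10% and 20%:

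- excluded: 7.7% to 16.7%
- median PFS: +0.8 to +2.3 months
- 24-month OS (all treated): +4.2 to +8.3 points
- highest ORR: 0.37/(1 − 0.167) = 44.4%, with r = 0

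With d = 10% and PFS medians of 6 to 11 months, an OS median of 12 months gives 22% to 27% excluded, and one of 30 months gives 7% to 9%.

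**5. The other reading.** If the rule means staying on SU for 6 months, exponential TTF with medians of 5.9 and 10.5 months loses 1 − 2^(−6/5.9) = 51% and 1 − 2^(−6/10.5) = 33% of patients. Median TTF becomes 11.9 and 16.5 months (each plus 6).

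**The case against.** The strongest reply is that no visible section applies the 6-month set to any endpoint. Section 6 says all patients are in the primary analysis, 8.1.1 and 8.1.2 name other groups, and the table shells in SAP 9.1 and 9.3 have a separate first-line SU column. Much of the SAP between 4.2.1 and 5.4 is redacted or not shown, and an assignment could be there. This stands as a limit: the bias is conditional on use. It does not remove the defect, because a set labelled for efficacy that contradicts the rest of the SAP has to be reconciled wherever the assignment sits. Reading section 6 as all patients within the efficacy set would simply apply the biased set.

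Other points stand in part:

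- The sizes rest on assumed OS medians and on treatment durations used in place of PFS. The upward direction for PFS and OS does not depend on these values.
- The SU-other-sequence label is not defined in the visible text, so whether it narrows the first-line analysis is unknown. This problem is distinct from the 6-month rule, although the same edit resolves both.
- The TTF definition does not mention death, so the plan does not say how a death on SU is handled. No separate TTF shift was computed under the milder reading.
- The extreme-value imputation for ORR in section 6 helps with missing responses but does not bring back patients excluded from the set.
- The protocol calls the study hypothesis-generating (8.11). The median and rate are still its main output, and SAP 4.1 intends the results to be extrapolated to patients across the region.

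**Conclusion.** The concern holds. As worded, SAP 4.1 conditions the efficacy set on surviving and staying in follow-up for 6 months after time zero. It disagrees with section 6 and with the populations in 8.1.1 and 8.1.2. Both primary endpoints are affected, so this must be fixed before analysis.

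If the set is used, plausible inputs give a median PFS about 1 to 2 months too long and 24-month OS about 4 to 8 points too high, with 8% to 17% of patients removed. These figures assume exponential event times, OS medians of 18 to 24 months and deaths as 5% to 20% of first events. The ORR shift also needs early deaths to respond less often than other patients. The loss of precision for ORR is minor. Reading the rule as 6 months on SU would make the effect on TTF much larger.

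**What to change.** - **SAP 4.1:** define the efficacy population as all eligible enrolled patients with at least one SU dose and no minimum follow-up.
- **Events and censoring:** count early deaths as events for PFS and OS, and censor dropouts at their last assessment. State explicitly how a death on SU enters TTF.
- **ORR:** keep patients without a response assessment in the denominator, and align the hot-deck rule in section 6 and 8.1.2 with this.
- **SAP 8.1.1 and 8.1.2:** name this set for first-line PFS, TTF and ORR. Define the SU-other-sequence group and use it for the combined endpoints only. Correct the ORR role in 8.1.2 to match the first-line objective.
- **Any 6-month set:** show it only as a labelled landmark description, with time counted from month 6.

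The cost is a few lines in SAP 4.1, 6, 8.1.1 and 8.1.2. No extra patients or data are needed. Reported medians and rates will be somewhat less favourable than under the 6-month rule.

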3.4. Study Design and Study Population

OPTIMISE is an international (AfME), prospective, non-interventional, non-controlled, observational multicenter study.

Patients would be enrolled from several AfME countries including Algeria, Morocco, Tunisia, Egypt, UAE, Qatar & South Africa.

Investigators will be specialists in charge of adv/mRCC. These sites involved (at least when performing feasibility) will be representative of their respective countries in terms of practice. Participating physicians will not be influenced in their decision making and routine proceedings in any way.

Primary outcome measure will assess progression free survival (PFS) in patients receiving the SU and in patients receiving a second line treatment post SU; as well as TTF for patients with adv/mRCC.

Patients will be enrolled when they start a treatment with SU on 1st line. Patients enrolled at SU initiation, will be followed-up whatever the post 2nd line SU- different sequence treatment is (AXI, other drugs, no further active treatment, (supportive care)). The possible 1st and 2nd line sequences of treatment under investigation (ie, patient pools) will be ([Figure 1](#)):

- SU-AXI.
- SU- other second line treatment (sorafenib, pazopanib, everolimus, temsirolimus, other).
- SU- not further active treatment (supportive care).

The study will include a prospective data collection:

- Prospective data will be collected for all patients enrolled in the study at SU-1st line level, irrespective of 2nd line sequence treatment, or no further active treatment.
- Prospective data in terms of medical treatment records will be collected for all 2nd line patients.

The inclusion period of eligible patients is planned for 12 months, with minimum of 1 year follow-up period. Patients will be followed-up from their enrollment to the end of the study follow-up period.

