4.2. Subgroups

4.2.1. Subgroups to meet primary and secondary objectives

- Compare efficacy parameters (PFS, OS) for the combined 1st line SU- 2nd line sequences according to the second line post SU :
 - SU in 1st line-Axitinib TKI in 2nd line
 - SU in 1st line- other TKI in 2nd line (sorafenib, pazopanib)
 - SU in 1st line/mTOR in 2nd line (temsirolimus, everolimus)

CCI [REDACTED]

- [REDACTED]
- [REDACTED]
- [REDACTED]
- [REDACTED]
- [REDACTED]

[figure not shown] 2);

- Incidence of other AEs (grade ≤ 2);
- Incidence of all AE per grade.
- AEs will be analyzed separately for AEs related to SU as solicited and unsolicited AE.
- **Discontinuation due to toxicity**
 - Proportion of patients who discontinued the treatment of interest, because of AEs;
 - Treatment duration until discontinuation for AEs;
- **Deaths**
 - Proportion of patients who died due to any cause, over the treatment period (including the 28 days after the treatment discontinuation) and along the study;
 - Cause of death (tumor-related, other cause).

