8.2. Safety and tolerability analyses

- **Role:**
To describe safety and tolerability of patients receiving the SU–other sequence”.
- **Population:**
Study population “SU – other sequence” patients
- **Endpoints:**
- Incidence of adverse events (AEs)
- Discontinuation
- Deaths
- **Statistical methods:**
Descriptive methods
- **Method for handling missing values:**
None-Observed-case analysis

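### The SAP's safety population admits only patients who had an adverse event, so AE proportions computed in it are inflated and an overall any-AE row is 100% by construction

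*SAP*

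**What the plan says.** SAP 4.1 gives the safety population as: "Include full analysis set who exhibited any adverse event after the first dose of SU". The efficacy population, defined just before it, does require a dose of SU (together with six months of follow-up). The safety definition instead requires an event.

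Protocol 3.3.3, secondary endpoint 7, is what the AE tables have to deliver: "Safety description with AE listing in patients receiving SU: frequencies of patients experiencing at least one AE will be displayed by body system". Its population is everyone given SU.

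The readable AE endpoints in the SAP, just before 5.4, include AE incidences by grade and this item: "Proportion of patients who discontinued the treatment of interest, because of AEs". No analysis set is attached to them in the visible text, and the start of that list is not visible.

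SAP 8.2, the safety analysis section, does not mention the 4.1 set. Its role is "To describe safety and tolerability of patients receiving the SU–other sequence" and its population is "Study population “SU – other sequence” patients".

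Two reporting rules in SAP section 4 also bear on this. One is "All summary tables will include the total number of subjects in the population that is being analysed". The other sets the precision of percentages: "where the percentage as whole numbers will be in parentheses".

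**The concern.** A safety set normally contains everyone exposed, so that the proportion with an event estimates risk in the exposed. Here patients without an event leave the denominator while every patient with one stays in the numerator. The resulting percentages describe how AEs are distributed among patients who had one, and they overstate the risk for a patient starting SU.

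Descriptive percentages are the whole output of endpoint 7, so the denominator matters even though no hypothesis test depends on it. Section 4 also puts the size of the analysed population on every table, so the choice of set will show in the report. An analyst who follows 4.1 and one who follows 8.2 could report different percentages from the same data.

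**Working it through.** **Inputs.** The set definition is from SAP 4.1. The counts are from the pre-filled AE shell in SAP 9.5, which has a single SU column with N = 85. They are dummy figures and are used only for illustration. The planned size of 140 is from Protocol 8.7. All 140 are taken as SU-treated, which is an assumption in line with the inclusion criteria.

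**Step 1: the shell's own figure.** 83/85 = 97.6%, as printed. That denominator includes 85 − 83 = 2 patients without an AE, so the shell was not laid out on the 4.1 set.

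**Step 2: the formula.** Let n be the number of SU-treated patients, q the share with any recorded AE after the first dose, and k the number with a particular AE. All k patients are in the 4.1 set, whose size is nq.

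- Proportion among all treated: k/n.
- Proportion in the 4.1 set: k/(nq) = (k/n) × (1/q).
- For any AE, k = nq, so the result is nq/nq = 100% for every q.

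The same 1/q applies to discontinuation because of AEs, since each such patient has an AE and so belongs to the set. It also applies separately to each body system. Those rows are inflated but not forced to 100%.

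**Step 3: shell counts on both denominators.** Factor = 85/83 = 1.024.

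| Row | Count | N = 85 | N = 83 (4.1 set) | At whole-percent precision |
|---|---|---|---|---|
| Any AE | 83 | 97.6% | 100% | 98 → 100 |
| Fatigue/asthenia | 69 | 81.2% | 83.1% | 81 → 83 |
| Mucositis/stomatitis | 50 | 58.8% | 60.2% | 59 → 60 |
| Diarrhea | 26 | 30.6% | 31.3% | 31 → 31 |
| Any grade 3/4 | 23 | 27.1% | 27.7% | 27 → 28 |

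**Step 4: planned size.** With m AE-free patients among 140, the factor is 140/(140 − m).

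- m = 7: 140/133 = 1.053
- m = 13: 140/127 = 1.102
- m = 28: 140/112 = 1.25

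These values of m show where the factor reaches about 1.05, 1.10 and 1.25. They are not forecasts.

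**Step 5: does SAP 8.2 settle the denominator?** The label *SU – other sequence* appears in several places with different implications:

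- SAP 8.1.1 lists it as a population for the survival analyses, whose roles include first-line PFS and TTF. That suggests a broad group.
- SAP 8.1.2 pairs it with response in patients receiving second-line treatment. That suggests a narrower one.
- SAP table 9.1 gives it a column separate from first-line SU and from the supportive-care sequence.

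Protocol 3.4 also lists a third pool, "SU- not further active treatment (supportive care"), and the readable text does not say whether those patients fall under the label. Section 8.2 therefore does not fix who is counted for endpoint 7.

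**The case against.** The strongest reply is that the 4.1 set is never used. In the readable text it appears only where it is defined, 8.2 names another population, and the shell's column includes AE-free patients. That stands as a limit: the inflation is conditional on tables being run on the set labelled for safety. It does not excuse the definition, because an analyst looking for the safety denominator would reasonably take the set with that name, and 8.2 offers no clear alternative.

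It can also be said that the effect is small. On the only counts available the factor is 1.02 and one of the five rows above does not move at whole-percent precision. The endpoint is descriptive, and Protocol 8.11 describes the study as hypothesis-generating. This also stands, and it lowers the priority.

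Three stronger readings are tempting, and the documents do not support them.

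- A reader might infer that endpoint 7 as a whole becomes 100%. It is displayed by body system, so only an overall any-AE row is forced to that value.
- A reader might infer that endpoint 7 has no analysis at all. Part of the SAP's AE endpoint text is not visible, and 8.1.1 uses the 8.2 label for first-line outcomes, so a second-line-only reading of 8.2 is not established.
- A reader might count the shell's N = 85 as a further specified population. It is dummy content that names no set, against 140 patients planned.

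**Conclusion.** The point holds in a limited form. The safety population in SAP 4.1 is wrong as written because it selects on having an AE. If it is used, an overall any-AE row is 100% by construction, and all other AE proportions, including AE-related discontinuation, are too high by 1/q. The factor is 1.02 on the shell's dummy counts, and 1.05 to 1.25 if between 7 and 28 of 140 treated patients have no recorded AE. The documents do not say where q will fall, so the effect on individual rates may be small.

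Separately, SAP 8.2 leaves the denominator for endpoint 7 unsettled. That is an ambiguity in the readable text, not proof that the analysis was omitted.

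This should be fixed. The consequence is a misstated or undefined percentage in a descriptive secondary endpoint, with no effect on a test decision. The arithmetic assumes that every patient counted in a row had that AE recorded after the first SU dose.

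**What to change.** - In SAP 4.1, replace the definition with: *Safety population: all enrolled patients who received at least one dose of SU, with or without an AE.*
- In SAP 8.2 and in the header of shell 9.5, name this set as the denominator for Protocol endpoint 7.
- Keep the *SU – other sequence* safety table, but report it as a separate subset, define the label, and say whether supportive-care patients are included.

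The cost is a text edit in three places, with no new data. AE percentages will be lower than in the 4.1 set, and any AE can fall below 100%. Compared with the 8.2 population the direction of change cannot be stated, because that population is not clear.
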